9.4.3.2 Comparison of the incidence of stroke, major bleeding, death

The incidence rate ratio for each event of interest (stroke, major bleeding and death; see [Table VIII](#) for derivation of events of interest) will be compared using a Cox regression model with OAC exposure (see [Table VII](#) for derivation of exposure sequences) considered as time-dependent variable adjusted for covariates. Covariates will be derived at index date as indicated in [Table XV](#).

Table XV. Derived variables for confounders

Variable	Definition
Age	Categorical variable (<80 years old / 80–90 / >90 years old) See Table III
Sex	Binary variable (Female / Male) See Table III
Prescriber's specialty at initiation of OAC	Categorical variable (Hospital-based physician/ City cardiologist/ Generalist practitioners/Other) See Table III
Having Malnutrition	Binary variable (Yes / No) See Table III
Risk of falls	Binary variable (Yes / No) See Table III
Frail patients	Binary variable (Yes / No) See Table V
Morbid obesity	Binary variable (Yes / No) See Table VI
At least one visit to a nursing home	Binary variable (Yes / No) See Table VI
Concomitant treatments	Binary variable (Yes / No) for each concomitant treatment listed in Table XIV

For example, for antiplatelet drugs, equals to “Yes” if the patient has at least one reimbursement for an antiplatelet drug in the 4 months before the index date
	
HAS-BLED score	Categorical variable (0, 1, 2, 3, ≥ 4) See Table VI
CHAD₂DS₂VASC score	Categorical variable (0, 1, 2, 3, 4, ≥ 5) See Table VI
Age adjusted Charlson Cormordity Index (ACCI) adapted to SNDS data	Categorical variable (0, 1-2, 3-4, ≥ 5) See Table VI XII

9.4.3.3 *Estimation of the AF annual standardized incidence rate and prevalence*

All the variables in [Table XVI](#) will be derived for all AF patients in France in 2016, 2017, 2018 and 2019.

Table XVI. Derived variables for incidence and prevalence

Variable	Definition
Incident AF patient	Binary variable (Yes / No) See Table X
Prevalent AF patient	Binary variable (Yes / No) Equals to “Yes” if the patient is diagnosed AF during the historical period Patients belonging to the study population

9.4.3.4 *To describe the use of oral anticoagulants (OACs) in AF patients initiating treatment (AF patients exposed to OAC therapy)*

Table XVII. Derived variables for OAC treatment pattern

Variable	Definition
New user of OAC (for all incident AF patients)	Binary variable (Yes/No) Equals to “Yes” if the patient receives at least one reimbursement of an OAC (VKA, apixaban, rivaroxaban or dabigatran) during the follow-up period, without use of any OAC in the 24 months prior to the first date of OAC delivery ATC codes: B01AA, B01AF02, B01AF01, B01AE07 Equals to “No” in other cases

VKA	Binary variable (Yes / No) Equals Yes if at least one reimbursement associated to VKA is identified during the follow-up period Equals to "No" in other cases. Same methodology for Apixaban, Rivaroxaban, Dabigatran
Number of sequence treatment	Categorical variable (1/2/3/4/5+) Equals to "1", "2", "3", "4" and "5+" if one only, two, three, four and five or more different OAC respectively, are identified in a discontinuous sequence during the follow-up period
Duration of each OAC	Continuous variable Equals to the sum of prescription duration for each OAC during the follow-up period (for duration calculation refer to table VII for start and end date of each OAC)
Switch of OAC treatment	Binary variable (Yes/no) Equal to 'Yes' if the patient has at least one reimbursement of a OAC different from the first OAC delivered Equal to 'No' if the patient has no reimbursement of a OAC different from the first OAC delivered or have permanent discontinuation of treatment
Temporary or permanent discontinuation	Binary variable (Yes/no) Equal to 'Yes' if the patient has at least 60 days without reimbursement of an OAC after the date of the first OAC delivery Equal to 'No' in the other case
Concomitant treatments	Binary variable (Yes/no) Equal to 'Yes' if the patient has at least one reimbursement of beta-blockers, antihypertensives, antiplatelet drugs, other anticoagulants, non-steroidal anti-inflammatory drugs (NSAIDs), oral corticoids, proton pump inhibitors, selective serotonin reuptake inhibitor antidepressants (SSRIs), systemic azole antifungals, CYP P450 inhibitors, protease inhibitors, lipid-lowering drugs, glucose-lowering drugs, antiarrhythmics during the follow-up period Equal to 'No' in other case
Type of delivery	Categorical variable (Hospital/Private medical practice) Equal to 'Hospital' if the variable PSE_STJ_COD (mode of practice) = 61, 62 Equal to 'Private medical practice' if the variable PSE_STJ_COD = 51, 55, 63, 64, 69.

Prescriber's specialty	Categorical variable (Hospital-based physician/ City cardiologist/ Generalist practitioners/Other) Equal to 'Hospital-based physician' if PSE_STJ_COD = 61, 62 Equal to 'City cardiologist' if the variable PSE_SPE_COD (medical specialty of the prescriber) = 3 and PSE_STJ_COD = 51, 55, 63, 64, 69. Equal to 'Generalist practitioners' if the variable PSE_SPE_COD = 1 and PSE_STJ_COD = 51, 55, 63, 64, 69. Equal to 'Other' if the variable PSE_SPE_COD not in 3 or 1.
-------------------------------	---

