Congestive heart failure (for ACCI derivation)	
Binary variable (Yes / No)
 
Derived based on (20,23)
 
Equals to "Yes" if the patient meets any criterion below on or in the 2 years prior to the index date:
 
 - Is hospitalized at least once with any diagnosis (i.e., main, related or associated diagnosis) of congestive heart failure 
ICD-10 codes: I110;I130;I132;I50
 
OR
 
 - Is covered by the LTD status for congestive heart failure at least one day 
ICD-10 codes: I110;I130;I132;I50
 
Equals to "No" in other cases

Peripheral vascular disease (for ACCI derivation)	
Binary variable (Yes / No)
 
Derived based on (20,23)
 
Equals to "Yes" if the patient meets any criterion below on or in the 2 years prior to the index date:
 
 - Is hospitalized at least once with any diagnosis (i.e., main, related or associated diagnosis) of peripheral vascular disease 
ICD-10 codes: I70.x, I71.x, I73.1, I73.8, I73.9, I77.1, I79.0, I79.2, K55.1, K55.8, K55.9, Z95.8, Z95.9
 
OR
 
 - Is covered by the LTD status for peripheral vascular disease at least one day 
ICD-10 codes: I70.x, I71.x, I73.1, I73.8, I73.9, I77.1, I79.0, I79.2, K55.1, K55.8, K55.9
 
Equals to "No" in other cases

Cerebrovascular disease (for ACCI derivation)	
Binary variable (Yes / No)
 
Derived based on (20,23)
 
Equals to "Yes" if the patient meets any criterion below on or in the 2 years prior to the index date:

- Is hospitalized at least once with any diagnosis (i.e., main, related or associated diagnosis) of cerebrovascular disease

ICD-10 codes: G45.x, G46.x, H34.0, I60.x, I61.x, I62.x, I63.x, I64.x, I65.x, I66.x, I67.x, I68.x, I69.x

OR

- Is covered by the LTD status for cerebrovascular disease at least one day

ICD-10 codes: G45.x, G46.x, H34.0, I60.x, I61.x, I62.x, I63.x, I64.x, I65.x, I66.x, I67.x, I68.x, I69.x

Equals to "No" in other cases

Moderate-to-severe

**renal disease (for
ACCI derivation)**

Binary variable (Yes / No)

Derived based on (20,23)

Equals to "Yes" if the patient meets any criterion below on or in the 2 years prior to the index date:

- Is hospitalized at least once with any diagnosis (i.e., main, related or associated diagnosis) of moderate-to-severe renal disease

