Solid metastatic tumor (for ACCI derivation)	
Binary variable (Yes / No)
 
Equals to “Yes” if the patient meets any criterion below on or in the 2 years prior to the index date:
 
 – Is hospitalized at least once with any discharge diagnosis (i.e., main, related or associated diagnosis) of metastatic tumor 
ICD-10 codes : C77.x, C78.x, C79.x, C80
 
OR
 
 – Is covered by the LTD status for metastatic tumor at least one day 
ICD-10 codes : C77.x, C78.x, C79.x, C80
 
Equals to “No” in other cases

Age adjusted Charlson Cormordity Index (ACCI) adapted to the SNDS data	
Continuous variable (point)
 
Derived based on (20,23)
 
Equals to the sum of:
 
 ○ 0 point if the variable History of diabetes equals to “Yes” ○ 0 point if the variable History of diabetes with complications equals to “Yes” ○ 0 point if the variable History of myocardial infarction equals to “Yes” ○ 2 points if the variable Heart failure equals to “Yes” ○ 1 point if the variable Peripheral vascular disease equals to “Yes” ○ 1 point if the variable Cerebrovascular disease equals to “Yes” ○ 1 point if the variable Moderate-to-severe renal disease equals to “Yes” ○ 2 points if the variable Mild liver disease equals to “Yes” ○ 3 points if the variable Moderate-to-severe liver disease equals to “Yes” ○ 1 point if the variable Chronic pulmonary disease equals to “Yes” ○ 2 points if the variable Dementia equals to “Yes”

	
 ○ 0 point if the variable Connective tissue disease equals to "Yes" ○ 0 point if the variable Ulcer disease equals to "Yes" ○ 2 points if the variable Hemiplegia equals to "Yes" ○ 1 point if the variable HIV-AIDS equals to "Yes" ○ 2 points if the variable Any tumor (including lymphoma and leukemia) equals to "Yes" ○ 11 points if the variable Solid metastatic tumor equals to "Yes" ○ 1, 2, 3, 4, 5 or 6 points if the variable Age is greater or equal than 50, 60, 70, 80 90 or 100 years old, respectively
ACCI group	
Categorical variable (0, 1-2pts / 3-4pts / ≥ 5 pts)
 
Derived based on ACCI define above
 
Equals to:
 
"0" if ACCI is equal to 0 (the patient has no comorbidities)
 
"1-2pts" if ACCI is greater than 0 and less or equal to 2
 
"3-4pts" if ACCI is greater than 2 and less or equal to 4
 
≥ 5pts" if ACCI is greater or equal than 10

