Bleeding history or predisposition (for HAS-BLED score derivation)	
Binary variable (Yes / No)
 
Equals to “Yes” if the patient is hospitalized with hospital-discharge summary with primary diagnosis of bleeding on or in the 2 years prior to the index date:
 
ICD-10 codes: D62, D683, D698, D699, H113, H313, H356, H431, H450, H922, I230, I312, I600-I616, I618-I621, I629, I850, I983, J942, K250, K252, K254, K256, K262, K264, K270, K272, K274, K276, K280, K282, K284, K286, K661, K920, K921, K922, M250, N020-N029, N421, N920, N921, N923, N924, N938, N939, N950, R040, R041, R042, R048, R049, R31, R58, S064, S065, S066, S260, S271, T792
 
Equals to “No” in other cases

Labile international normalized ratio (INR) (for HAS-BLED score derivation)	
Binary variable (Yes / No)
 
Not applicable to SNDS data (INR results are not captured in SNDS databases).

Elderly (for HAS-BLED score derivation)	
Binary variable (≤ 65 years old / > 65 years old)

Drugs predisposing to bleeding or alcohol concomitantly (for HAS-BLED score derivation)	
Binary variable (Yes / No)
 
Variable Drugs equals to “Yes” if the patient has at least one drug dispensation for antiplatelet agents (acetylsalicylic acid: B01AC06 ATC code, clopidogrel: B01AC04 ATC code) or NSAIDs (M01A ATC code) in the 4 months before the index date.
 
OR

	
Variable Alcohol equals to “Yes” if the patient is hospitalized with any discharge diagnosis (i.e., main, related or associated diagnosis) of all causes related to alcohol on or in the 2 years prior to the index date:
 
ICD-10 codes : E244, E512, F10, G312, G621, G721, I426, K292, K70, K860, R780, T51, X45, X65, Y15, Y90, Y91, Y573, Z502, Z714, Z721.
 
Equals to “No” in other cases

HAS-BLED score	
Continuous variable (between 1 and 9)
 
Derived based on (19)
 
Equals to sum of:
 
 ○ 1 point if the variable Hypertension equals to “Yes” ○ 1 or 2 points if the variable Abnormal renal and liver function equals to “Yes” (1 point each) ○ 1 point if the variable Stroke equals to “Yes” ○ 1 point if the variable Bleeding equals to “Yes” ○ 1 point if the variable Labile INRs equals to “Yes” ○ 1 point if the variable Elderly equals to “>65 years old” ○ 1 or 2 points if the variable Drugs or alcohol equals to “Yes” (1 point each)

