Contraindications to OAC	
Binary variable (Yes/No)
 
Equals to “Yes” if the patient presents at least one contraindication to OAC among the followings:
 
 ● End-stage renal disease on dialysis ● Diseases of the blood and blood-forming organs ● Certain disorders involving the immune mechanism ● Recent history of acute bleeding gastric or duodenal ulcer ● Hepatic cirrhosis or fibrosis or liver failure 
Equals to “No” in other cases.

Chronic renal disease (for contraindications to OAC)	
Binary variable (Yes / No)
 
Equals to “Yes” if the patient meets any criterion below on or in the 2 years prior to the index date:
 
 – A main or related discharge diagnosis of renal transplantation 
ICD-10 code: Z94.0
 
OR

- A renal transplantation surgery
CCAM: JAEA003, HNEA002
 OR
- Is hospitalized at least once with any diagnosis (i.e., main, related or associated diagnosis) of chronic renal disease
ICD-10 codes: N18.x
 OR
- Is covered by the LTD status for chronic renal disease at least one day
ICD-10 codes: N18.x
 OR
- Has received ≥ 19 hemodialysis sessions in inpatient or outpatient settings
CCAM codes : JVJF004, JVJF008, JVRP004
PRS codes : 2121, 2122, 2123, 2126, 2129, 2131, 2132, 2134, 2135, 2136, 2139, 2147, 2334
GHM codes : 11K021, 11K022, 11K023, 11K024, 11K02J, 28Z03Z, 28Z04Z
 OR
- Has received ≥ 1 peritoneal dialysis session in inpatient or outpatient settings
CCAM codes: JVJB001, JVRP007, JVRP008, YYYY007
PRS codes : 2124, 2125, 2127, 2128, 2137, 2138, 2140, 2142, 2143, 2144, 2145, 2146
GHM codes : 28Z01Z, 28Z02Z

Equals to "No" in other cases.

Chronic renal disease requiring dialysis (for contraindications to OAC)	Binary variable (Yes / No) Equals to "Yes" if the patient meets any criterion below on or in the 2 years prior to the index date: 
 - Has the value "Yes" for the variable Chronic renal disease AND - Has at one reimbursement for a dialysis session performed at hospital or in outpatient settings CCAM codes: JVJB001, JVJF004, JVJF008, JVRP004, JVRP007, JVRP008, YYYY007
--	---

	
PRS codes : 2121, 2122, 2123, 2124, 2125, 2126, 2127, 2128, 2129, 2131, 2132, 2133, 2134, 2135, 2136, 2137, 2138, 2139, 2140, 2142, 2143, 2144, 2145, 2146, 2147, 2334
 
GHM codes : 28Z01Z, 28Z02Z, 28Z03Z, 28Z04Z, 11K021, 11K022, 11K023, 11K024, 11K025
 
Equals to “No” in other cases

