3.3. Comparison of the incidence of stroke, major bleeding, death

Table A10. Risk of stroke, major bleeding or death in AF incident patients

	Event		Crude risk ¹		Adjusted risk ^{2,*}	
	n	%	HR	[95%CI]	HR	[95%CI]
Risk of stroke						
Exposure to DOACs	xx	(x.x)	x.xx	[x.xx-x.xx]	x.xx	[x.xx-x.xx]
Exposure to Apixaban	xx	(x.x)	x.xx	[x.xx-x.xx]	x.xx	[x.xx-x.xx]
Exposure to Dabigatran	xx	(x.x)	x.xx	[x.xx-x.xx]	x.xx	[x.xx-x.xx]
Exposure to Rivaroxaban	xx	(x.x)	x.xx	[x.xx-x.xx]	x.xx	[x.xx-x.xx]
Unexposed to OAC**	xx	(x.x)	x.xx	[x.xx-x.xx]	x.xx	[x.xx-x.xx]
Exposure to VKA	xx	(x.x)	ref		ref	
Risk of major bleeding						
Exposure to DOACs	xx	(x.x)	x.xx	[x.xx-x.xx]	x.xx	[x.xx-x.xx]
Exposure to Apixaban	xx	(x.x)	x.xx	[x.xx-x.xx]	x.xx	[x.xx-x.xx]
Exposure to Dabigatran	xx	(x.x)	x.xx	[x.xx-x.xx]	x.xx	[x.xx-x.xx]
Exposure to Rivaroxaban	xx	(x.x)	x.xx	[x.xx-x.xx]	x.xx	[x.xx-x.xx]
Unexposed to OAC**	xx	(x.x)	x.xx	[x.xx-x.xx]	x.xx	[x.xx-x.xx]
Exposure to VKA	xx	(x.x)	ref		ref	
Risk of death						
Exposure to DOACs	xx	(x.x)	x.xx	[x.xx-x.xx]	x.xx	[x.xx-x.xx]
Exposure to Apixaban	xx	(x.x)	x.xx	[x.xx-x.xx]	x.xx	[x.xx-x.xx]
Exposure to Dabigatran	xx	(x.x)	x.xx	[x.xx-x.xx]	x.xx	[x.xx-x.xx]
Exposure to Rivaroxaban	xx	(x.x)	x.xx	[x.xx-x.xx]	x.xx	[x.xx-x.xx]
Unexposed to OAC**	xx	(x.x)	x.xx	[x.xx-x.xx]	x.xx	[x.xx-x.xx]
Exposure to VKA	xx	(x.x)	ref		ref	

AF : Non Valvular Atrial Fibrillation; HR: hazard ratio; 95%CI: 95% confidence interval

Note: For considering DOAC treatment in models, two regressions models will be performed for this table: one model with "Exposure to DOACs" as independent variable; second model with exposure for each molecule within the class of DOAC (Apixaban, Dabigatran, Rivaroxaban).¹From a time-dependant exposure to OAC Cox proportional hazards model

²From a time-dependant exposure to OAC and time-fixed covariates Cox proportional hazards model;

*Adjusted on the following covariates at index date: age (<80, 80-90, >90 years old), sex, having malnutrition, risk of falls, morbid obesity, history of stroke, history of major bleeding, at least one visit to a nursing home, history of dementia, each concomitant treatments

**Unexposed to OAC correspond to the period where the patients are not exposed to OAC.

Same table will be presented for sensitivity analyses:

- with integration of 2020 data

- with 30 days and 90 days of maximal number of days allowed for being refilled

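### The Cox models adjust for renal disease only partly, through one point in each of two categorised scores, so confounding by coded renal disease may remain

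*SAP*

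**What the plan says.** SAP 9.4.3.2 sets the source of adjustment: "Covariates will be derived at index date as indicated in" Table XV. That table lists age, sex, prescriber's specialty, malnutrition, risk of falls, frailty, morbid obesity, nursing-home visit, each concomitant treatment and three scores. HAS-BLED is entered as "Categorical variable (0, 1, 2, 3, ≥ 4"), CHA2DS2-VASc as "Categorical variable (0, 1, 2, 3, 4, ≥ 5"), and ACCI in the bands 0, 1-2, 3-4 and 5 or more.

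Renal disease has one point in two of the three scores:
- HAS-BLED (9.4.3.1): "1 or 2 points if the variable Abnormal renal and liver function equals to" yes, one point for each organ.
- ACCI (Table VI, 9.4.1): "1 point if the variable Moderate-to-severe renal disease equals to" yes.
- CHA2DS2-VASc has no renal item.

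Four renal variables are derived. Two are score components: moderate-to-severe renal disease (Table VI) and abnormal renal function (Table XII). The other two, chronic renal disease and chronic renal disease requiring dialysis (Table XII), serve a descriptive contraindications variable that includes "End-stage renal disease on dialysis". That variable is not in Table XV.

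Section 9.7.4.2 names no renal term and no score, but refers to Table XV for all confounders. The Table A10 footnote begins "Adjusted on the following covariates at index date: age (<80, 80-90, >90 years old), sex, having malnutrition, risk of falls, morbid obesity" and lists no renal term or score either. The sensitivity analyses in 9.7.6 add no renal term. Section 9.9 notes that biological and clinical data are absent but does not mention kidney function.

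**The concern.** A confounder must bear on both treatment and outcome. By the SAP's own definitions, renal disease counts towards a bleeding score and dialysis counts against any OAC. The second link concerns treated versus untreated time, which the models estimate as unexposed against VKA. Dialysis patients stay in that comparison: the criteria table in protocol 3.2.1 lists contraindications to OAC among the exclusions, but SAP 9.2.3.2 does not, and the two need reconciling.

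VKA is the reference in every model. If renal disease is more common in one exposure state than another and the scores absorb only part of its effect, the rest passes into the exposure hazard ratio. In a cohort this large the confidence interval would be too narrow to signal the problem.

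**Working it through.** The plan gives no figure to reproduce here. Three checks follow.

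**1. When does the renal point change a modelled category?** This uses only the SAP scoring rules.

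- HAS-BLED, other items totalling 0, 1, 2 or 3: the renal point raises the category by one, as any other single point would. At 4 or more the category does not change.
- ACCI, reading the top band as its label says (5 or more): the point changes the band only when the other points total 0, 2 or 4. At 1, 3 and 5 or more it is invisible.
- ACCI gives 3 points for age 70-79 and 4 for age 80-89. A patient aged 70-79 with no other scored condition is in band 3-4 with renal disease (3 + 1 = 4) or without it (3).
- Table VI labels the top band as 5 or more but derives it as 10 or more. A patient aged 80-89 whose only scored condition is renal disease totals 4 + 1 = 5 and, as written, has no band.

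In one assumed case mix, the renal point changes the ACCI band for about 30% of renal patients, and HAS-BLED absorbs it without a change of category in about 6.5%.

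**2. Size if nothing adjusted for renal disease.** None of these inputs is in the documents: renal disease 15%; VKA share 25% without renal disease and s with it; renal hazard ratio h; true DOAC-versus-VKA HR 1.00.

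- P(renal | VKA) = 0.15s / (0.15s + 0.85 × 0.25)
- P(renal | DOAC) = 0.15(1 − s) / (0.15(1 − s) + 0.85 × 0.75)
- Apparent HR ≈ [1 + P(renal | DOAC)(h − 1)] / [1 + P(renal | VKA)(h − 1)]

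For s = 0.60 and h = 2.0: P(renal | VKA) = 0.0900/0.3025 = 0.298; P(renal | DOAC) = 0.0600/0.6975 = 0.086; HR ≈ 1.086/1.298 = 0.837.

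**3. Size with the Table XV scores.** Two simulations under the null (400,000 patients each; about 40,000 and 43,000-47,000 events) used the same values of s and h with different assumed case mixes.

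| s, h | No renal adjustment (formula) | Table XV, case mix A | Table XV, case mix B |
|---|---|---|---|
| 0.35, 1.5 | 0.970 | 0.978 | 0.987 |
| 0.45, 1.5 | 0.944 | 0.971 | 0.986 |
| 0.45, 2.0 | 0.898 | 0.941 | 0.971 |
| 0.60, 2.0 | 0.837 | 0.895 | 0.926 |

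On the log scale the share of bias left is ln(Table XV HR)/ln(formula HR), for example ln 0.895/ln 0.837 = 0.62. Across the table it runs from 0.24 to 0.74. It is rough, because the simulated values carry sampling error of about 0.01.

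Adding a perfectly measured renal indicator in case mix A gives 0.997, 1.009, 1.010 and 1.006. In case mix B a milder input (VKA share 30% in renal disease, h = 1.5) gives 0.990 without the term and 0.995 with it (SE 0.011).

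A third, large-sample calculation varied renal prevalence over 5-20%, the odds ratio of VKA use given renal disease over 2-4, and h over 1.0-3.0:

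- h from 1.5 to 3.0: Table XV gives 0.977 down to 0.871. With a renal term it gives 0.979-0.981 throughout. The part due to the missing term runs from 0.977/0.981 = 0.996 (0.4%) to 0.871/0.979 = 0.890 (11%).
- h = 1.0: Table XV gives 0.989 to 1.011 against 0.980-0.981 with the term, a ratio of 1.008 to 1.031. Here the scores credit renal disease with an effect it does not have, and the error has the opposite sign.

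The constant 0.98 that remains with the term does not vary with the renal effect, so it has another source in that case mix.

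With no link between renal disease and the VKA/DOAC choice (25% VKA in both groups, h = 2.0), the HR is 1.012 with or without the renal term. The unexposed-versus-VKA contrast was not simulated.

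**The case against.** The strongest reply is that the SAP does adjust for renal disease. HAS-BLED and ACCI both carry it. Several other HAS-BLED items also enter separately: antiplatelets, NSAIDs and antihypertensives as concomitant treatments, and stroke and bleeding history through 9.7.4.2. The score terms can therefore recover part of the renal effect instead of forcing it to equal that of any other point. Frailty may add more, though the SAP does not list the components of the frailty index. This stands: adjustment is partial, not absent.

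A reader might infer from the Table A10 and A11 footnotes that renal disease is not adjusted for at all. The documents do not support that. Sections 9.4.3.2 and 9.7.4.2 both point to Table XV, and the footnotes also omit prescriber's specialty and frailty, so they read as abbreviated table notes. A model on the footnote list departs further from 1, but in the third calculation it already gives about 0.95 with no renal effect at all, so that departure should not be put down to kidney disease.

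A reader might also infer that the DOAC-versus-VKA hazard ratios are biased in favour of DOAC. The documents link dialysis to OAC as a class, not to choosing VKA over DOAC; every input behind that direction is assumed.

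Finally, the comparison is a secondary objective, and the primary objective is descriptive.

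**Conclusion.** The point holds as an avoidable gap in adjustment, not as demonstrated bias. The SAP derives renal indicators, uses renal disease in a bleeding score and treats dialysis as bearing on OAC use, yet its models see renal disease only through two coarsened sums. Confounding by coded renal disease may remain, most directly for unexposed versus VKA, whose size was not estimated, and for DOAC versus VKA if renal disease also shifts that choice.

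Under a true null, the Table XV hazard ratio for DOAC versus VKA runs from about 0.99 to 0.87 over the assumed inputs that link renal disease to both VKA use and outcome. It is unaffected where there is no link to the choice of drug. The documents cannot place the study within that range or settle the direction. The near-null results with a renal term assume perfect measurement, so they should not be read as what the study would achieve.

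**What to change.** 1. In Table XV and 9.7.4.2, add *Moderate-to-severe renal disease* (Table VI) and *Chronic renal disease requiring dialysis* (Table XII) as separate binary covariates at index date. Keep the three scores. The dialysis coefficient is then an increment over coded renal disease.
2. Before use, reconcile the code lists. Within the Table VI definition "of moderate-to-severe renal disease", the diagnosis list has Z49.1 and Z49.2 but the dialysis criterion has Z94.1 and Z94.2. The last hospital-group code is 11K025 in the Table XII dialysis variable and 11K02J in the other renal variables.
3. Align the footnotes of Tables A10 and A11 and the list in 9.7.4.2 with Table XV, and correct the derivation of the ACCI top band.
4. In 9.9, state that claims codes capture diagnosed renal disease, not kidney function, and that covariates are fixed at index while exposure varies, so some confounding will remain.

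The cost is SAP wording and two degrees of freedom, in a study expecting about 1 million (protocol 3.3) to 1.3 million (SAP 9.5) exposed patients. Both variables are already specified, so no further data are needed.
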